3.3. Study Day/Relative Day

Study Day 1 or Day 1 refers to the day of ATIMP administration. All efficacy and safety assessments at all visits will be assigned a day relative to this date.

Study day (or relative day) for a visit is defined as:

- Visit date (date of Study Day 1) +1 day, if the visit date is on or after Day 1
- Visit date date of Day 1, if the visit date is before Day 1

3.4. Visit Windows

The following rules are applied to assign actual visits to analysis visit windows other than baseline. If a subject has two or more actual visits in 1 visit window, the visit closest to the target day will be used as the protocol visit for that visit window. The additional visit(s) will not be used in the summaries or analyses, but they can be used for determination of clinically important outcomes. If two actual visits are equidistant from the target day within a visit window, the later visit is used. All assignments will be made in chronological order. Once a visit date is assigned to a visit window, it will no longer be used for a later time point.

Table 1: Visit Windows

Visit Window Label	Time Interval	Target Day
Baseline	-6 Months - < Day 1	< Day 1
Day 1	Day 1	Day 1
Day 2	Day 2	Day 2
Day 4	Day 3 – Day 5	Day 4
Week 1	Day 6 – Day 10	Day 8
Week 2	Day 11 – Day 20	Day 15
Week 4	Day 21 – Day 36	Day 29
Week 6	Day 37 – Day 59	Day 43
Week 12	Day 60 – Day 127	Day 85
Week 24	Day 128 – Day 225	Day 169

3.5. Data Handling Rules

In the case where a variable is recorded as ">x", ">x", "<x" or "<x", for analysis purposes a value of x will be taken. Where a range of values is quoted the midpoint of the range will be taken. For example, if a laboratory safety parameter is reported as being below the limit of quantification or <x, the value of the limit will be used in the calculation of summary statistics. The recorded value will be reported in listings.

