Up to 10 mL of blood will be sampled to measure immune response. Antibody responses to AAV capsid proteins will be investigated by ELISA at baseline and at 4 weeks, 3 months, and 6 months following ATIMP administration.

(iii) Evaluation of biodistribution

Systemic biodistribution of vector genomes will be assessed by PCR analysis of tears (a compressed cellulose sponge placed under the eye lid until swollen), saliva (a minimum of 100 µL) and serum (1 mL) at 1 day and at 4 weeks following intraocular ATIMP administration. The test will be carried out in the [REDACTED].

Gene Therapy for Achromatopsia (*CNGB3*)

(iv) Assessment of visual function and retinal imaging

Assessment of visual function and retinal imaging will be performed as outlined in Section 5.6 (Trial Assessments). They will be carried out with the same methods applied for the baseline tests (see section 8.6 for details) to allow direct comparison of the data sets. These assessments will be scheduled over a period of a day for visits at day 1, day 3, day 7, week 2, week 4 and week 6 after surgery, and up to 4 days for baseline examinations, and 3 months, 6 months following ATIMP administration. For day 1 and 3 refraction cannot reliably be measured. Therefore, the most recent refraction measurement will be used.

All participants (adults and children) will need to be able to perform reliable visual acuity testing and SD-OCT imaging, which are the principal clinical assessments both for safety and efficacy. Other clinical assessments will be undertaken as appropriate for the ability of individual participants, since there is wide variation in the abilities of individual children to perform such tests reliably; the evaluations for individuals may be restricted to those tests that they are able to perform reliably.

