5.3. Clinical Laboratory Tests

Clinical laboratory tests will be displayed for the subjects included in the safety analysis set. Hematology, clinical chemistry, glucose, serology and polymerase chain reaction (PCR) laboratory tests will be presented.

Summary statistics of hematology and clinical chemistry observed values and change from baseline by parameter (unit) will be summarized by age group, dose level and overall.

All hematology and clinical chemistry values will be listed.

Serology data will be listed and summarized at each assessment by age group, dose level and overall.

All PCR values will be summarized by tissue and listed.

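### SAP 3.5 sets below-limit results to the limit without exempting PCR or serology, so a numeric summary could not separate absence of vector or antibody from presence at the limit

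*SAP*

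**What the plan says.** SAP 3.5 covers any variable recorded with a less-than or greater-than sign: "for analysis purposes a value of x will be taken". Its worked example is the laboratory case, "if a laboratory safety parameter is reported as being below the limit of quantification or <x", where "the value of the limit will be used in the calculation of summary statistics". The listings are treated differently: "The recorded value will be reported in listings".

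SAP 5.3 names the tests to which this would apply: "Hematology, clinical chemistry, glucose, serology and polymerase chain reaction (PCR) laboratory tests will be presented". For the two assays at issue it says "Serology data will be listed and summarized at each assessment by age group, dose level and overall" and "All PCR values will be summarized by tissue and listed". Neither sentence names a statistic, a count of samples at or above the limit, or a seroconversion rate. PCR is to be broken down by tissue; visit and dose level are not mentioned for it.

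On the purpose of the PCR samples, Protocol 5.4.2.3 (iii) says "Systemic biodistribution of vector genomes will be assessed by PCR analysis" of tears, saliva and serum, taken 1 day and 4 weeks after administration. Protocol 5.4.2.4 describes the result as a number of vector genome copies. Protocol 5.4.2.1 anticipates that most participants will have no detectable antibody against AAV8 before treatment.

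**The concern.** For routine haematology and chemistry, few values fall below a limit and putting the limit in their place does little harm. Biodistribution and anti-capsid antibody differ, because the first question is whether anything is there at all. Below-limit results are expected to be the majority for baseline antibody. They are plausible for PCR too, since Protocol 4.1.5.2 expects at most minimal amounts of vector in other organs. The substituted value could then decide most of the table.

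What is at stake is how the biodistribution and serology summary tables read. Someone looking for spread of vector outside the eye, or for its disappearance between Day 1 and Week 4, would see a positive number where the laboratory had reported only that the result was below the limit.

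**Working it through.** The plan gives no figure to reproduce, so the rule is applied directly.

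**Inputs**
- Substitution rule: a result below L becomes L (SAP 3.5).
- PCR result: a numeric copy count (Protocol 5.4.2.4), measured at Day 1 and Week 4 only (Protocol 5.4.2.3 (iii) and Table 2).
- Sample size: up to 36 participants, 18 per phase, in cohorts of 3 that may grow to 6 (Protocol 4.3 and 5.7, Table 1).
- Assumptions: the assay limits are not given, so L is the unit. The reporting format is not given either, so a below-limit sample is assumed to be recorded as less than L or as below the limit of quantification. The summary is assumed to be numeric.

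**All results below L.** Every value becomes L. Mean = nL/n = L; median = minimum = maximum = L; SD = 0. This holds for n = 3, 6, 18 and 36. Three different situations give this one table: no vector in anyone, traces between zero and L in everyone, and exactly L copies in everyone. The minimum can never be less than L, so a Week 4 table can show a fall towards the limit but not a fall below it.

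**One result of 10L, the rest below L (illustration).** Mean = [10L + (n − 1)s]/n, where s is the substituted value.

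| n | s = L (SAP) | s = L/2 | s = 0 |
|---|---|---|---|
| 6 | 15/6 = 2.50L | 12.5/6 = 2.08L | 10/6 = 1.67L |
| 18 | 27/18 = 1.50L | 18.5/18 = 1.03L | 10/18 = 0.56L |
| 36 | 45/36 = 1.25L | 27.5/36 = 0.76L | 10/36 = 0.28L |

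The median and minimum equal s in every cell, so they are set by the convention and not by the data. The spread across columns shows how far the mean depends on a choice that the data cannot settle. None of the columns is the true mean.

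**Baseline antibody.** If more than half of a group is below the limit, as the protocol expects, the baseline median and minimum are both L by construction.

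**What a count would say.** With none of n at or above the limit, the exact two-sided 95% upper bound is 1 − 0.025^(1/n): 70.8% for n = 3, 45.9% for n = 6, 18.5% for n = 18 and 9.7% for n = 36. This depends on no substituted value.

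**The case against.** The strongest reply is that the harm rests on an inferred table. SAP 5.3 specifies summary statistics of observed values and change from baseline for haematology and chemistry only. The mean and SD convention in SAP 4 belongs to subject information, and that section also provides for frequency tables of categorical data. SAP 1 places the mock-ups in a separate document, which may already contain a detection count. A reader might infer that no detection frequency is planned. The SAP text is silent, which is weaker than that. This part stands, and the point is therefore conditional on a numeric summary.

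Three other stronger readings are tempting and are not supported.
- That the rule reports vector in participants in whom none was detected. It applies to results recorded as less than x or below the limit of quantification. Below quantification is not the same as absent, and the rule does not say what happens to a result recorded as negative or not detected.
- That the distortion can be sized. If 10% of samples were at 10L and the rest were truly zero, the rule would give 0.9 × 1 + 0.1 × 10 = 1.9L against 1.0L, or 90% too high. Against half-limit substitution it is 1.9L versus 0.9 × 0.5 + 0.1 × 10 = 1.45L, or 31%. No passage supports that scenario, and for vector spread the limit errs in the cautious direction.
- That an antibody rise would be understated. From below the limit to 10L reads as 10-fold with L and 20-fold with L/2, but the SAP plans no change from baseline for serology.

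It is also true that nothing is lost from the record. Listings keep the recorded result, and PCR can yield at most 36 × 3 × 2 = 216 of them, so absence or clearance can be read there. Neither assay enters the primary outcome, the SAP's list of efficacy outcomes or a stated decision rule.

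The core remains: the SAP does state a rule, its own example is the laboratory case, and PCR and serology are not exempted.

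**Conclusion.** The concern holds in conditional form and is minor. Under SAP 3.5 and 5.3 as written, a numeric summary of PCR results that are all below the limit shows the limit in every location statistic, with SD 0. It cannot separate absence or clearance from presence at the limit. Baseline antibody summaries are affected in the same way.

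This rests on two assumptions that the documents do not settle: that PCR and serology are summarised numerically, and that below-limit samples are recorded in a form which triggers the rule. The size in mixed data cannot be stated without the assay limits and reporting format; the table above is illustration only. A reader might infer that the biodistribution question cannot be answered from this trial. That does not follow, because the listings answer it. The fault is confined to summary tables, and the primary safety outcome is untouched.

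**What to change.** In SAP 3.5, exempt PCR and serology from the substitution and leave the rule as it is for every other variable. Confining the rule to haematology and chemistry would go too far, since it would also remove it from efficacy measures recorded with a less-than or greater-than sign.

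In SAP 5.3, make the main summary of both assays the number and percentage of samples at or above the assay limit, by visit and dose level and, for PCR, by tissue. Add median and range, with below-limit values shown as `<limit`. State the limit for each assay, and say that a result recorded as not detected counts as below it.

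The cost is one revised table per assay and no new data. If the separate mock-ups already carry such counts, the exemption and a sentence in SAP 5.3 are enough.

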3.6. Imputation Rules for Missing Adverse Event Dates

Partial adverse event (AE) onset dates will be imputed as follows:

- If the onset date of an AE is only missing the day, it will be imputed as:
- First day of the month that the AE occurred, if month/year of the onset of the AE is different than the month/year of ATIMP administration
- The day of ATIMP administration, if the month/year of the onset of AE is the same as month/year of ATIMP administration and month/year of the AE resolution date is different
- The day of ATIMP administration or day of AE resolution date, whichever is earliest, if month/year of the onset of AE and month/year of ATIMP administration and month/year of the AE resolution date are same
- If the onset date of an AE is missing both day and month, it will be imputed to the earliest of:
- January 1 of the year of onset, as long as this date is on or after ATIMP administration
- Month and day of ATIMP administration, if this date is the same year that the AE occurred
- Last day of the year if the year of the AE onset is prior to the year of ATIMP administration,
- The AE resolution date.
- Completely missing onset dates will not be imputed.

Partial AE resolution dates not marked as ongoing will be imputed as follows:

- If the resolution date of an AE is missing day only, it will be set to the earliest of the last day of the month of occurrence of resolution or the day of the date of death, if the death occurred in that month.
- If the resolution date of an AE is missing both day and month, it will be set to the earliest of December 31 of the year or the day and month of the date of death, if the death occurred in that year.

Completely missing resolution dates will not be imputed.

4. SUBJECT INFORMATION

Summary statistics (arithmetic mean, standard deviation [SD], median, minimum and maximum for continuous variables) will be presented by age group and dose level. Frequency tables for categorical data will also be provided.

4.1. Demographics and Baseline Characteristics

Table 2 list the demographic and baseline characteristic variables that will be summarized by age group, dose level (see Table 3) and overall.

Table 2: Demographic Variables and Baseline Characteristics

Continuous Variables:	Summary Type	
Age (years)	Descriptive statistics (N. mean	
Weight (kg)	Descriptive statistics (N, mean, SD, median and range	
Height (cm)	[minimum and maximum]).	
Body Mass Index (BMI) (kg/m ²)	[minimum and maximum]).	
Categorical Variables		
Sex (male, female)		
Race ^a (American Indian or Alaska Native, Asian, Black or	Frequency distribution with the number and percentage of subjects in each category.	
African American, Native Hawaiian or other Pacific		
Islander, White, Multiple)		
Ethnicity (Hispanic or Latino, not Hispanic or Latino)		
Study Eye (left, right)		

^a If multiple race categories are indicated, the Race is recorded as 'Multiple'.

4.2. Definition of Subgroups

Descriptive summaries of safety and/or efficacy may be done by considering, but not limited to, the following subgroups:

Table 3: Subgroups

Subgroup	Definition
Age Group	• Adults
	• Children (<16 years old [United Kingdom] or <18 years old
	[United States])
Dose Level	• Low
	Intermediate
	• Other
	High
Country	United Kingdom
	United States
Sex	• Female
	• Male

4.3. Disposition Information

A subject will be considered to have completed the study if the subject completes the Week 24 visit.

The number of subjects in the following disposition categories will be summarized throughout the study by age group, dose level and overall for safety analysis set.

- Subjects who were administered ATIMP
 - Subjects who completed the study
 - Subjects who prematurely discontinued from the study and their reasons for discontinuation

Listings will also be provided.

4.4. Genetic Testing

A listing of genetic testing data based on screening for CNGB3 mutations prior to enrollment will be provided.

4.5. ATIMP Administration

ATIMP administration volume and study eye data will be summarized. All ATIMP administration data will be listed.

4.6. Medical History and Ophthalmic History

Medical history findings will be summarized using Medical Dictionary for Regulatory Activities (MedDRA) by Primary System Organ Class/High Level Term.

Ophthalmic history apart from the study condition will be summarized and an accompanying listing will be provided.

4.7. Prior and Concomitant Medications

Prior and concomitant medications will be coded using the World Health Organization Drug Dictionary (WHO-DD). Prior medications are defined as any therapy initiated before the day of ATIMP administration. Concomitant medications are defined as any therapy used on or after the day of ATIMP administration, including those that started before and continue on or after ATIMP administration.

Summaries of prior and concomitant medications by Anatomical Therapeutic Chemical (ATC) term will be presented by dose level, age group and overall. The proportion of subjects who receive each medication will be summarized as well as the proportion of subjects who receive at least 1 medication.

Concomitant medications of interest (e.g., medication for management of inflammation/corticosteroids) will also be provided.

4.8. Protocol Deviations

Subjects with major protocol deviations will be summarized and an accompanying listing will be provided.

5. SAFETY ANALYSES

5.1. Primary Safety Outcome

The proportion of subjects who experience the primary safety outcome and the corresponding 95% confidence interval (CI) using for the binomial proportion based on the normal approximation with continuity correction will be provided (by age group, dose level and overall). The primary safety outcome will also be listed.

A similar analysis will also be conducted for dose-limiting events (DLEs).

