4.3.2.2.4 Additional considerations

In the event of a DLE in one of the 3 participants at a given dose, the cohort will be expanded at the same dose level. The IDMC will review the safety data and confirm that additional participants may be treated at this dose. The IDMC may recommend that the same dose of ATIMP is administered to additional participants. The dose escalation will continue until IDMC are comfortable on review of the accumulating data, to recommend a maximum dose to be administered to children, or 3 participants have been administered the highest dose without any DLEs, or until at least 2 participants among a cohort of 3 to 6 participants experience DLEs (i.e., $\geq 33\%$ of patients with a DLE at that dose level), in which case the recommended dose will be the level below this toxic dose. In the event that 1 or 2 DLEs are seen at the first dose level, the IDMC may recommend administering a lower dose to that described in the protocol to a cohort of participants.

Table 1: Dose escalation table

Number of DLEs			
Low dose			
Participants 1-3	Participants 4-6	Action	Details
0/3		Increase	Give intermediate dose to next cohort of participants
1/3		Remain	Give low dose to another cohort of participants (Pt 4-6)
$\geq 2/3$		Stop	MTD not found. Consider lower dose
	$\leq 1/6$	Increase/stop	Has higher dose been tried? No: Give intermediate dose to next cohort of participants

Gene Therapy for Achromatopsia (CNGB3)

			Yes: MTD found – low dose
	≥ 2/6	Stop	MTD not found. Consider lower dose
Intermediate dose			
Participants 1-3	Participants 4-6	Action	Details
0/3		Increase	Give high dose to next cohort of participants
1/3		Remain	Give intermediate dose to participants 4-6
≥ 2/3		Decrease/stop	Give low dose to 3 more participants. If 6 participants already had low dose, stop. MTD found – low dose.
	≤ 1/6	Increase/stop	Has higher dose been tried? No: Give high dose to participants 1-3 Yes: MTD found – intermediate dose
	≥ 2/6	Decrease/stop	Give low dose to participants 4-6. If 6 participants already had low dose, stop. MTD found – low dose
High dose			
Participants 1-3	Participants 4-6	Action	Details
0/3		Remain	MTD found – give high dose to participants in confirmation phase
1/3		Remain	Give high dose to participants 4-6
≥ 2/3		Decrease/stop	Give intermediate dose to participants 4-6. If 6 participants already had intermediate dose, stop. MTD found – intermediate dose
	1/6	Stop	MTD found – high dose

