5.7 Sample Size

This is a Phase I/II trial to establish safety and assess indicators of potential efficacy of the ATIMP, therefore there is no formal sample size calculation. The trial will enrol up to 36 participants (up to 18 in the dose escalation phase and up to a further 18 in the confirmatory phase), as described in section 4.3.2.2. The limited number of participants is necessitated by the rare nature of the disease under investigation. We estimate that inclusion of up to 36 participants will be sufficient to determine the safety and tolerability of the intervention.

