5.10.3.2 Statistical Methods – Primary Outcome Analysis

The primary outcome is safety of subretinal administration of the ATIMP defined as any of the below occurring during the 6 weeks following administration, at least possibly related to the ATIMP, not surgery alone:

- Reduction in visual acuity by 15 ETDRS letters or more
- Severe unresponsive inflammation
- Infective endophthalmitis
- Ocular malignancy
- Grade III or above non-ocular SUSAR (see section 5.11.3)

The number of DLEs at each dose level will be summarised by cohort and overall.

It is anticipated that the ATIMP will be administered at the MTD in up to 15 participants (6 adults in the dose escalation phase and up to 18 further adults and children in the confirmatory safety phase). Safety data relating to these participants will allow estimation of an upper bound for the true event rate through a 95% confidence interval.

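### With no events, the SAP's 95% interval for the primary safety outcome has an upper limit of only 1/(2n), some four to seven times below the exact limit

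*SAP*

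**What the plan says.** For the share of participants who meet the primary safety outcome, SAP 5.1 plans a 95% interval "using for the binomial proportion based on the normal approximation with continuity correction will be provided (by age group, dose level and overall"). It adds that dose-limiting events (DLEs) will be analysed in a similar way. It gives no exact or score alternative and no rule for a group with zero events, and neither does any other section of the two documents.

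Protocol 5.10.3.2 states the purpose of the interval. For participants treated at the maximum tolerated dose (MTD), it says: "Safety data relating to these participants will allow estimation of an upper bound for the true event rate through a 95% confidence interval".

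The groups are small. Protocol 4.3.2.2.4 works with cohorts of 3 to 6 and treats zero events as a normal outcome: escalation may end once "3 participants have been administered the highest dose without any DLEs". Protocol 5.7 caps the trial at 36 participants.

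**The concern.** The natural reading of SAP 5.1 is the Wald interval with continuity correction. Its width comes from the estimated standard error, which is zero when no events are seen. Only the continuity correction is then left, and that does not depend on the confidence level. The interval therefore tells the reader almost nothing about the uncertainty in a zero count, which is where an upper bound is most needed.

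That bound is the only inferential quantity the protocol promises for its primary outcome. A report of no events in 24 participants with an upper limit of about 2% would be read as strong evidence of safety, in a dose-escalation gene therapy trial whose expansion phase may enrol children. The data would not support that reading.

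**Working it through.** The documents give no numerical bound and assume no event rate, so there is no figure of the plan's own to reproduce. The SAP formula is applied directly and compared with the exact binomial interval.

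**Inputs**
- Method: normal approximation with continuity correction (SAP 5.1).
- Level: 95%. SAP 5.1 does not state sidedness. Two-sided is assumed (z = 1.96), as SAP 6 does for efficacy.
- Group sizes: 3 and 6 (Protocol 4.3.2.2.4); 18 per phase and 36 overall, both maxima (Protocol 5.7); 15 or 24 at the MTD. Protocol 5.10.3.2 gives the last as "up to 15 participants (6 adults in the dose escalation phase and up to 18 further adults and children in the confirmatory safety phase"), but 6 + 18 = 24, so both are shown.
- True event rates used for coverage: illustrative assumptions.

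**Formula.** With x events in n and p = x/n, the SAP interval is p ± (1.96·√(p(1−p)/n) + 1/(2n)).

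**Zero events.** The square root is 0, so the upper limit is 1/(2n). The raw lower limit is −1/(2n), or 0 if truncated. The exact two-sided upper limit is 1 − 0.025^(1/n); the exact one-sided 95% limit is 1 − 0.05^(1/n). The last column is (1 − 1/(2n))^n, the chance of seeing no events if the true rate equalled the SAP limit.

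| n | SAP upper | Exact two-sided | Exact one-sided | Exact two-sided ÷ SAP | P(0 events at SAP limit) |
|---|---|---|---|---|---|
| 3 | 16.7% | 70.8% | 63.2% | 4.2 | 0.58 |
| 6 | 8.3% | 45.9% | 39.3% | 5.5 | 0.59 |
| 15 | 3.3% | 21.8% | 18.1% | 6.5 | 0.60 |
| 18 | 2.8% | 18.5% | 15.3% | 6.7 | 0.60 |
| 24 | 2.1% | 14.2% | 11.7% | 6.8 | 0.60 |
| 36 | 1.4% | 9.7% | 8.0% | 7.0 | 0.60 |

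One minus the last column is the one-sided confidence the SAP limit actually carries: about 40%.

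**One or two events.** For 1/3: √(0.3333 × 0.6667/3) = 0.2722; 1.96 × 0.2722 + 0.1667 = 0.7001; the limits are 0.3333 ± 0.7001.

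| Events/n | SAP interval | Exact interval |
|---|---|---|
| 1/3 | −36.7% to 103.3% | 0.8% to 90.6% |
| 1/6 | −21.5% to 54.8% | 0.4% to 64.1% |
| 2/6 | −12.7% to 79.4% | 4.3% to 77.7% |
| 1/24 | −5.9% to 14.2% | 0.1% to 21.1% |
| 1/36 | −4.0% to 9.5% | 0.1% to 14.5% |

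**Coverage of the nominal 95% SAP interval**, by summing binomial probabilities over the counts whose interval contains the true rate. For example, with n = 3 and a rate of 20%, the interval misses at 0 events (0.8³ = 0.512) and at 3 events (0.2³ = 0.008), so coverage is 0.480.

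| n | Rate just below 1/(2n) | Rate just above | Higher rate |
|---|---|---|---|
| 3 | 15%: 99.7% | 20%: 48% | 30%: 63% |
| 6 | 8%: 99.9% | 10%: 47% | 20%: 72% |
| 15 | 3%: about 100% | 5%: 54% | 10%: 79% |
| 24 | 2%: about 100% | 3%: 52% | 5%: 71% |
| 36 | 1%: about 100% | 2%: 52% | 5%: 84% |

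The exact interval covered at least 95% at every combination tried (n of 3, 6, 15, 18, 24 and 36; rates from 2% to 30%).

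**How likely is a zero cell?** At an assumed true rate of 10%, no events occur with probability 0.9³ = 73% for n = 3 and 0.9⁶ = 53% for n = 6. Splitting by age group makes zero cells more likely.

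**The case against.** The strongest reply is that nothing in the trial turns on this interval. Dose decisions rest on DLE counts and committee review, the analysis is described as descriptive, no hypothesis is tested, and the events are listed so that anyone can recompute a limit. It is true that no dose decision depends on the interval. But a descriptive interval labelled 95% should still behave roughly like one, and the protocol says it "will allow estimation of an upper bound for the true event rate through a 95% confidence interval". Listings do not correct a published limit.

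A second reply is that the sentence in SAP 5.1 is garbled and might mean a Wilson score interval with continuity correction. That interval also rests on a normal approximation and does not collapse: its zero-event upper limits are 69.0% for n = 3, 25.4% for n = 15, 17.2% for n = 24 and 12.0% for n = 36. The SAP names neither Wilson nor a score method, however, and its words are the usual description of the corrected Wald interval. If Wilson was meant, the text still has to say so.

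Four qualifications stand:
- Coverage is erratic rather than uniformly near 50%. It is at or above nominal just below 1/(2n), drops sharply just above, and partly recovers at higher rates (92% for n = 24 at a rate of 10%).
- The upper limit is not always too low. At 1/3 and 2/6 it exceeds the exact one.
- The rule that stops a dose at two DLEs applies to escalation cohorts of 3 to 6. It does not show that the larger MTD, age-group or overall rows will have at most one event.
- The protocol promises its upper bound for the MTD group, so the n = 15 and n = 24 rows matter most for that promise. SAP 5.1 nevertheless extends the same interval to every dose level and age group.

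**Conclusion.** The concern holds. With zero events the SAP upper limit is 1/(2n) by algebra, whatever the event rate or the sidedness. It is 4.2 to 7.0 times below the exact two-sided 95% limit at the group sizes considered. For the MTD group the plan would report 3.3% instead of 21.8% (n = 15) or 2.1% instead of 14.2% (n = 24). With one event the upper limit is still too low in the larger groups (1/24: 14.2% against 21.1%), and lower limits are negative.

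The conclusion rests on reading SAP 5.1 as the continuity-corrected Wald interval. The coverage figures and the zero-cell probabilities also rest on illustrative event rates, because the documents assume none. This must be corrected before the primary outcome is reported: it misstates the one bound the protocol promises, and at zero events it does so towards overstating safety.

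**What to change.** In SAP 5.1, replace the normal-approximation interval with the two-sided 95% exact (Clopper-Pearson) interval for the primary safety outcome and for DLEs, at every dose level, in each age group and overall. State the sidedness. A Wilson score interval would also remove the collapse. The exact interval is preferred because its coverage does not fall below the nominal level, which suits a safety bound. Record the change among the SAP changes and apply it whatever counts are observed.

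Separately, reconcile the MTD total in Protocol 5.10.3.2 (15 against 6 + 18 = 24), so that the denominator of the promised bound is clear.

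The cost is one line of SAP text and one option in the program, with no new data. The reported upper limits will be wider and less favourable, in line with what groups of this size can show.
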